10.5 AEs of Special Interest

An AE of special interest (AESI) is any AE that a regulatory authority has mandated be reported on an expedited basis, regardless of the seriousness, expectedness, or relatedness of the AE to the administration of a product or compound. Systemic injection reactions and thrombotic microangiopathy (TMA) have been identified as AESI and should be reported within 24 hours using the AE eCRF (██████). These will not be reported to ██████ unless they become SAEs.

10.5.1 Systemic Injection Reactions

Systemic injection reactions have been observed with KZR-616 and other proteasome inhibitors and are considered AESIs.

Systemic injection reactions have included a number of signs and symptoms including fever, chills, myalgia, facial swelling or flushing, dizziness, headache, nausea, vomiting, weakness, hypotension, chest tightness, and shortness of breath, as well as abnormalities in laboratory values (e.g., creatinine, transaminases) and blood pressure. However, the relative roles of the immunoproteasome versus constitutive proteasomes to these specific events are not known. Therefore, terms such as the NCI-CTCAE terms of ‘infusion-related reaction,’ ‘cytokine release syndrome,’ ‘acute infusion reaction,’ or ‘allergic or hypersensitivity reaction’ should not be used. Instead, each sign or symptom should be recorded as an individual AE. If multiple signs or symptoms occur with a given systemic injection-related event, each sign or symptom should be recorded separately with its own level of severity.

Management of systemic injection reactions is described in [Section 7.1.3](#).

10.5.2 Thrombotic Microangiopathy (TMA)

Cases of TMA, including TTP and HUS, have been described with the nonspecific proteasome inhibitors, bortezomib, carfilzomib, and ixazomib. The clinical presentation of TMA typically includes fever, microangiopathic hemolytic anemia (with schistocytes on blood smear), thrombocytopenia, renal failure, purpura, and neurological manifestations. Patients should be monitored for signs and symptoms of TTP/HUS. If the diagnosis is suspected, interrupt treatment with study drug and evaluate (refer to [Section 9.1](#)). Missed doses should be addressed as per [Section 7.1.4](#). If the diagnosis of TTP/HUS is excluded, study drug may be resumed. If the diagnosis is confirmed, study drug must be permanently discontinued (refer to [Section 9.2](#)).

10.6 Unexpected Adverse Reactions

10.6.1 Unexpected Adverse Reaction Definition

An unexpected adverse reaction is any untoward and unintended response that is related to the administration of the study drug at any dose and that is not consistent with the applicable product information (e.g., investigators brochure for an unauthorized investigational medicinal product or summary of product characteristics for an authorized product).

All suspected unexpected serious adverse reactions (SUSARs) will be subject to expedited reporting. The sponsor and/or the CRO shall ensure that all relevant information about a SUSAR that is fatal or life-threatening is reported to the relevant competent authorities and IEC/IRB within 7 days after knowledge by the sponsor of such a case and that relevant follow-up information is communicated within an additional 8 days. All other SUSARs will be reported to the relevant competent authorities and IEC/IRB within 15 days after knowledge by the sponsor of such a case. All investigators should follow up SUSARs until the event is resolved or until, in the opinion of the investigator, the event is stabilized or determined to be chronic. Post study SUSARs that occur prior to completion of the 12 weeks follow-up must be reported by the investigator to the sponsor.

10.7 Data Monitoring Committee

To enhance the safety and integrity of the study data, a study-specific DMC consisting of principal investigators, medical monitors, and Kezar Life Sciences (hereafter, Kezar) designees will be convened to review the accumulating safety data for the study.

For Phase 1b, safety review will occur for each cohort as it completes the first 4 weeks of treatment. The first safety review by the DMC will occur after the first 6 patients have been enrolled and received study drug and progressed to Week 4. Decisions to escalate, expand, or modify dose level(s) or frequency will depend on review of safety data by the DMC.

The DMC will review cumulative Phase 1b study data and provide a recommendation for the Phase 2 dose.

For Phase 2, the DMC will convene and review cumulative data on a periodic basis to be defined in a separate DMC charter.

The specific responsibilities and composition of the DMC are outlined in a separate DMC Charter. In addition, the details of outputs provided for the meetings will be referenced in the separate document.

11 STATISTICS

11.1 Endpoints

11.1.1 Phase 1b Endpoints

Primary Endpoints:

- Safety and tolerability of KZR-616 as assessed by changes in physical examination, safety laboratory findings, 12-lead ECGs; incidence and severity of AEs and SAEs; and the evaluation of other safety information collected and summarized by protocol specified time points along with a summary of change from baseline at each protocol specified time point

Secondary Endpoints:

- The RP2Ds of KZR-616 as determined by evaluation of safety parameters, PK, PD, and DLTs by the DMC
- Plasma PK parameters, including C_{max} , T_{max} , AUC, and other applicable parameters will be summarized for KZR-616 and its metabolites

Exploratory Endpoints:

- The efficacy of KZR-616 in patients with SLE with and without nephritis will be assessed through changes in lupus disease assessments and changes from baseline in laboratory measures
- The level of proteasome inhibition in whole blood and PBMCs, as measured by both a cleavable fluorogenic substrate enzymatic assay and a subunit-specific proteasome active site ELISA
- The proteomic and pharmacogenomic activity of KZR-616 will be assessed through ex vivo analysis of whole blood and PBMC samples
- Serum cytokine levels and circulating leukocytes will be measured in blood samples collected on Day 1 of Weeks 1, 5, 17, and 25

11.1.2 Phase 2 Endpoints

Primary Endpoint:

- The number of patients with a 50% reduction in UPCR after 24 weeks of treatment when compared to baseline

Secondary Endpoints:

- Safety and tolerability of KZR-616 as assessed by the incidence, nature, and severity of AEs

-
- The number of patients with a partial renal response (PRR) after 24 weeks of treatment as defined by:
 - a) A 50% reduction of UPCR and/or reduction of UPCR to < 1.0 if the baseline UPCR was < 3.0 or a 50% reduction of UPCR and/or reduction of UPCR to < 3.0 if the baseline was ≥ 3.0
 - b) eGFR of ≥ 60 mL/min/1.73 m² or no worsening of eGFR from baseline of $\geq 25\%$
 - c) No use of prohibited medication
 - The number of patients with a complete renal response (CRR) after 24 weeks of treatment as defined by:
 - a) UPCR of ≤ 0.5
 - b) eGFR of ≥ 60 mL/min/1.73 m² or no worsening of eGFR from baseline of $\geq 25\%$
 - c) Prednisone (or equivalent) < 10 mg
 - d) No use of prohibited medication
 - Time to $\geq 50\%$ reduction in UPCR from baseline
 - Time to CRR
 - Time to PRR
 - Time to UPCR of ≤ 0.5 from baseline
 - The number of patients with UPCR of ≤ 0.5 at 24 weeks
 - The number of patients with daily prednisone (or equivalent) dose ≤ 10 mg
 - Change from baseline in levels of autoantibodies (e.g. ANA, anti-dsDNA) and complement at 24 weeks
 - Changes in corticosteroid use from baseline

Exploratory Endpoints:

- The level of proteasome inhibition in whole blood and PBMCs, as measured by both a cleavable fluorogenic substrate enzymatic assay and a subunit-specific proteasome active site ELISA
- Change from baseline in SLEDAI-2K score, CLASI, and 28 joint count and changes from baseline in laboratory measures
- The proteomic and pharmacogenomic activity of KZR-616 will be assessed through ex vivo analysis of whole blood and PBMC samples
- Serum cytokine levels and circulating leukocytes will be measured in blood samples collected on Day 1 of Weeks 1, 5, 17 and 25

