Patients who do not fulfill Dosing Criteria ([Section 7.1](#)) may miss up to 2 consecutive doses in Phase 1b or Phase 2 or patients may miss up to 4 total doses in Phase 1b or up to 6 total doses in Phase 2 for any reason (e.g. AE, scheduling, emergency). Upon resumption of dosing, subsequent doses should be timed according to the original dosing schedule based on Day 1. Patients who cannot resume dosing within 2 weeks of the first missed dose or who miss more than 4 total doses in Phase 1b or 6 total doses in Phase 2 must permanently discontinue KZR-616 unless the doses in question were missed based on Study Stopping Rules ([Section 9.1](#)). If doses were missed due to implementation of Study Stopping Rules, then the patient should be discussed with the medical monitor to evaluate if KZR-616 should be discontinued. Any dose modifications should be discussed with the medical monitor and documented in the eCRF.

If study medication is permanently discontinued due to an AE, standard therapy and planned assessments (see Schedule of Assessments, [Section 14.1](#), Appendix A, and [Section 14.2](#), Appendix B, for Phase 1b and Phase 2, respectively) should continue for the protocol specified time period.

7.2 **Prior and Concomitant Medications**

A concomitant medication is any prescription or over-the-counter preparation, including vitamins and supplements. Any concomitant therapies must be recorded on the eCRF. Except as described below, prior and concomitant medication use will be recorded for the 60 days prior to screening until the last follow-up visit.

All prior SLE treatment (e.g., immunosuppressants, antimalarials, biologics) will be recorded, including corticosteroid use, from at least the previous 24 weeks prior to screening. When possible, all prior biologics should be recorded.

SLE Disease-Related Concomitant Medications

Patients should continue all concomitant medications related to SLE therapy throughout the study, as outlined in Inclusion/Exclusion Criteria (Section 5.2), this section (Section 7.2), and Table 3.

- All immunosuppressant therapies and antimalarial agents should be continued at a stable dose except when change is deemed necessary by the treating physician or clinical investigator, or if access is limited due to supply issues (see also Section 7.2.2).

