7.2.1 Excluded Concomitant Medications

The use of any investigational agents or devices is prohibited.

Plasma exchange/plasmapheresis and live-attenuated vaccines are excluded.

Please refer to [Section 14.5](#), Appendix E, for a list of excluded medications and associated wash-out periods.

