11.3.5 Criteria for Evaluation – Efficacy Analyses

Phase 2:

Assessment of Primary and/or Secondary Endpoints

Please see [Section 11.1.2](#) for a listing of secondary endpoints for Phase 2.

Rate of renal response will be assessed at 24 weeks. Renal response will be classified as complete, partial [50% reduction in UPCR], or no renal response. Summary statistics (e.g., total number of patients with observed data, mean, median, SD, min, max for continuous endpoints; for binary endpoints: total number of patients observed, number of patients with the event of interest, percent) will be provided by dose in Phase 1b and for all patients combined in Phase 2. The primary efficacy endpoint in Phase 2 is percent of patients with 50% reduction in UPCR after 24 weeks of treatment when compared to baseline. The null hypothesis is that the percentage is $\leq 20\%$; the alternative hypothesis is that the percentage is $> 20\%$. The test of hypotheses will be carried out with an exact binomial test. The KZR-616-002 Statistical Analysis Plan contains details of the planned analysis.

Phase 1b and Phase 2: Exploratory Endpoints:

The efficacy of KZR-616 on SLE will be assessed using changes from baseline in study administered questionnaires/disease assessment tools and changes from baseline in laboratory measures.

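### As written in the protocol, the tested Phase 2 primary endpoint has no medication condition, although PRR and CRR do, so a UPCR halved after excluded or non-permitted added therapy counts as a response

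*Combined protocol and SAP*

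**What the plan says.** Section 11.1.2 gives the Phase 2 primary endpoint as "The number of patients with a 50% reduction in UPCR after 24 weeks of treatment when compared to baseline". The synopsis, Section 3.2 and Section 11.3.5 state it in the same UPCR-only form. Section 11.3.5 sets a null response rate of at most 20% and says: "The test of hypotheses will be carried out with an exact binomial test". It then refers onward: "The KZR-616-002 Statistical Analysis Plan contains details of the planned analysis". Section 11.3.1 gives the SAP precedence over the protocol.

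In the same list in Section 11.1.2, item (c) of PRR and item (d) of CRR read "No use of prohibited medication". The other UPCR-only endpoints, such as "The number of patients with UPCR of ≤ 0.5 at 24 weeks", have no such item.

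The medication rules are elsewhere:

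- Section 7.2 says that immunosuppressants and antimalarials "should be continued at a stable dose except when change is deemed necessary by the treating physician or clinical investigator", or if supply is limited, and then cross-refers to Section 7.2.2.
- Section 7.2.2 (Phase 2) bars added immunosuppressants except after a EuroLupus cyclophosphamide course. It allows regimen changes for unavailability, and dose modification for documented toxicity or unavailability.
- Section 7.2.1 says "The use of any investigational agents or devices is prohibited", excludes plasma exchange and live vaccines, and points to Appendix E for excluded drugs.
- Section 9.2 lists non-permitted concurrent therapy as a reason for which a patient may stop study drug.

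**The concern.** There is no control arm, and every patient is on background immunosuppression. If therapy is added and UPCR then halves, the data cannot separate that fall from an effect of KZR-616. The protocol accepts this reasoning for PRR and CRR, where prohibited medication rules out a response, but does not apply it to the one endpoint that has a null hypothesis and a test.

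At stake is how the primary response rate can be read. Section 2.5 anticipates pivotal lupus nephritis studies on the strength of Phase 2 safety and efficacy, so the rate will be used. Because Section 11.4 says the study is not powered by hypothesis testing, the issue is interpretability rather than a failed confirmatory test.

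**Working it through.** **Does any other protocol text make such a patient a non-responder?**

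- Sections 7.2, 7.2.1, 7.2.2 and Appendix E govern conduct. None ties a breach to response status.
- Section 9.2 makes stopping study drug possible, not mandatory, and says nothing about response.
- Section 11.2.2 defines safety, PK and PD populations only. No efficacy or per-protocol population would remove the patient.
- Section 11.3.6 includes patients whatever their duration of treatment and imputes nothing unless otherwise specified.

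So the protocol text does not.

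**Can such a patient have a Week 25 UPCR?** Yes, if still in assessment. Section 7.1.4 provides that "If study medication is permanently discontinued due to an AE, standard therapy and planned assessments" continue for the specified period. A patient who stays on study drug after a breach also keeps the visit schedule. A patient who leaves the study would usually have no Week 25 value: Section 9.3 lists no 24-hour urine at the withdrawal visit, and Section 11.3.6 uses data only up to withdrawal.

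**Does PRR supply the missing count?** Not in aggregate. Its UPCR item is wider than a halving. For example, a fall from 1.2 to 0.9 is (1.2 − 0.9)/1.2 = 25%, yet it meets PRR item (a) because baseline is below 3.0 and the result is below 1.0.

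**Size, as illustration.** There is no figure in the plan to reproduce: it gives no alpha, power or rate of added therapy. Inputs from the documents are n = 20 (Section 5.1) and p0 = 0.20 (Section 11.3.5). Assumed one-sided alpha is 0.05 or 0.025.

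With X ~ Binomial(20, 0.20), P(X ≥ k) is the sum over j from k to 20 of C(20, j) × 0.2^j × 0.8^(20−j):

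| Responders | p |
|---|---|
| ≥ 7 | 0.0867 |
| ≥ 8 | 0.0321 |
| ≥ 9 | 0.0100 |

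The smallest successful counts are therefore 8 at 0.05 and 9 at 0.025. One reclassified patient moves 8/20 (p = 0.032) to 7/20 (p = 0.087), or 9/20 (p = 0.010) to 8/20 (p = 0.032).

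Now suppose KZR-616 adds nothing, m of the 20 receive added therapy and respond at rate r, and the rest respond at 20%. Then P(success) = Σ over j of P(Bin(m, r) = j) × P(Bin(20 − m, 0.2) ≥ k − j).

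| Threshold k | r | m = 0 | m = 1 | m = 2 |
|---|---|---|---|---|
| 8 | 0.5 | 3.2% | 4.5% | 6.3% |
| 8 | 1 (upper bound) | 3.2% | 6.8% | 13.3% |
| 8 | 0 (counted as non-response) | 3.2% | 2.3% | 1.6% |
| 9 | 0.5 | 1.0% | 1.5% | 2.2% |
| 9 | 1 (upper bound) | 1.0% | 2.3% | 5.1% |
| 9 | 0 (counted as non-response) | 1.0% | 0.7% | 0.4% |

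Check of one cell (k = 8, m = 1, r = 0.5): 0.5 × P(Bin(19, 0.2) ≥ 7) + 0.5 × P(Bin(19, 0.2) ≥ 8) = 0.5 × 0.0676 + 0.5 × 0.0233 = 0.0454. The value r = 0.5 borrows the figure in Section 2.2 for standard regimens at about one year. It is an assumption for patients who add therapy within 24 weeks.

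**The case against.** The strongest reply is that the SAP holds the details and prevails. Non-responder rules often sit there, so the protocol cannot show how such a patient will be analysed. This stands, and it limits the point to the protocol text.

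A second reply is that the split may be deliberate. All the UPCR-only endpoints lack the condition and both composite responses have it, and counting UPCR regardless of medication is a legitimate choice. This also stands as a possibility, but the protocol never states it. Section 11.3.5 blurs the line further by glossing partial response as a 50% UPCR reduction, though that does not attach the PRR medication item to the primary endpoint.

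Third, the route is narrow. Section 7.2.2 bars most changes, Section 7.1.4 continues standard therapy without authorising additions, and withdrawals before Week 14 can be replaced. This stands as a limit on frequency.

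Fourth, anyone who halves UPCR meets PRR item (a), so a primary responder who is not a PRR responder must have failed on eGFR or medication. With 20 patients this is visible in listings. That is true at patient level, but the two reported counts would not show it.

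A reader might also infer that Sections 7.2 and 7.2.2 contradict each other. The discretionary wording in Section 7.2 is looser, but it ends by pointing to Section 7.2.2. What is missing is a statement of which governs.

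**Conclusion.** The gap in the protocol is real and worth closing, as a should-fix item with medium confidence. The definitional finding rests on the text alone. Its practical size is unknown, because the documents give no rate of added therapy.

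Two stronger readings are tempting and not supported. One is that the trial will in fact credit such patients as responders; the SAP that would settle this was not available. The other is that the test's error rate is seriously inflated. Alpha, m and r are all assumed. At r = 0.5, three of the four illustrative probabilities stay below their assumed nominal levels (4.5% against 5%; 1.5% and 2.2% against 2.5%), and only 6.3% exceeds its level. The largest figures, 13.3% and 5.1%, require both patients with added therapy to respond. That one patient can move the p-value is true of any classification question at n = 20.

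What remains is that, with no control arm, a UPCR fall after non-permitted therapy would be attributed to KZR-616 in the only tested endpoint. The term prohibited medication is also not defined clearly enough for PRR and CRR: Section 7.2.1 uses the word for investigational agents and devices, Appendix E speaks of excluded treatments, and neither says whether a change barred by Section 7.2.2 is covered.

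**What to change.** In Sections 11.1.2 and 11.3.5, count as a primary non-responder any patient who, before the Week 25 UPCR:

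- (a) used a therapy excluded by Section 7.2.1 or Appendix E, other than a live vaccine; or
- (b) added or increased a non-steroid immunosuppressant except as Section 7.2.2 permits, namely the regimen and up-titration after a EuroLupus course, a regimen change for unavailability, or a dose modification for documented toxicity or unavailability.

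Use (a) and (b) as the definition of prohibited medication for PRR and CRR, and state that Section 7.2.2 governs in Phase 2.

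Report two sensitivity analyses: the UPCR-only count, and a count that also treats a systemic steroid start or increase for flare as non-response. Apply the rule to time to at least 50% UPCR reduction, or waive it there explicitly, so that endpoint and the primary are consistent by design. If the SAP already has such a rule, a citation in Section 11.1.2 is enough.

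The cost is wording only; Appendix B already collects concomitant medications at each visit. The primary response rate may be lower, and the rule is conservative if the 20% benchmark counted responses regardless of medication. Therapy changes that Section 7.2.2 permits stay in the primary count, so some confounding remains.

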Pharmacodynamics: Blood samples for the determination of proteasome activity in whole blood and peripheral blood mononuclear cells will be assessed in blood samples collected as follows:

Phase 1b – Day 1 of Week 1 and Week 5, before dosing and 4 hours after

Phase 2 – Day 1 of Week 1, before dosing and 4 hours after injection, and Day 1 of Week 5, before dosing

Biomarkers: Blood samples for the determination of serum cytokine levels and circulating leukocytes will be measured in blood samples collected as follows:

Phase 1b – Day 1 of Weeks 1, 5, 17, and 25

Phase 2 – Day 1 of Weeks 1, 17, 25, and 37

Pharmacogenomics:

Gene expression (RNA) profiling – Blood samples collected as follows:

Phase 1b – Day 1 of Weeks 1, 5, 17, and 25

Phase 2 – Day 1 of Weeks 1, 17, 25, and 37

DNA genotyping – Day 1 of Week 1

Endpoints

Phase 1b:

Primary Endpoint:

- Safety and tolerability of KZR-616 as assessed by incidence, nature, and severity of AEs

Secondary Endpoints:

- The RP2Ds of KZR-616 as determined by evaluation of safety parameters, PK, PD, and DLTs by the DMC
- Plasma PK parameters, including maximum plasma concentration (C_{max}), time to maximum plasma concentration (T_{max}), area under the plasma concentration-time curve (AUC), and other applicable parameters will be calculated for KZR-616

Phase 2:

Primary Endpoint:

- The number of patients with a 50% reduction in UPCr after 24 weeks of treatment when compared to baseline

Secondary Endpoints:

- Safety and tolerability of KZR-616 as assessed by the incidence, nature, and severity of AEs
- The number of patients with a partial renal response (PRR) after 24 weeks of treatment as defined by:
 - a) A 50% reduction of UPCr and/or reduction of UPCr to < 1.0 if the baseline UPCr was < 3.0 or a 50% reduction of UPCr and/or reduction of UPCr to < 3.0 if the baseline was ≥ 3.0
 - b) eGFR of ≥ 60 mL/min/1.73 m² or no worsening of eGFR from baseline of $\geq 25\%$
 - c) No use of prohibited medication
- The number of patients with a complete renal response (CRR) after 24 weeks of treatment as defined by:
 - a) UPCr of ≤ 0.5
 - b) eGFR of ≥ 60 mL/min/1.73 m² or no worsening of eGFR from baseline of $\geq 25\%$

-
- c) Prednisone (or equivalent) ≤ 10 mg
 - d) No use of prohibited medication
 - Time to $\geq 50\%$ reduction in UPCR from baseline
 - Time to CRR
 - Time to PRR
 - The number of patients with UPCR of ≤ 0.5 at 24 weeks

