 4. At least one of the following at Screening per central lab:
 - a) Positive ANA test (1:80 or higher) or
 - b) Anti-dsDNA antibodies elevated to above normal (i.e., positive results); or
 - c) Anti-Smith antibody at screening elevated to above normal (i.e., positive results)
 5. Active nephritis with UPCR ≥ 1.0 measured in 24-hour urine collection
 6. Currently receiving one or more immunosuppressive agents (see [Section 7.2](#) for allowed background medications and [Section 14.5](#), Appendix E for excluded medications) that has been stable for dose and route of administration for ≥ 8 weeks prior to Baseline. If patient is also on corticosteroids then must be on a stable dose for ≥ 2 weeks prior to Baseline
 7. Renal biopsy within 2 years of the Screening visit with a histologic diagnosis of LN (ISN/RPS) Classes III, IV-S or IV-G, (A) or (A/C) +/- Class V; for biopsies > 1 year before the Screening visit, one of the following must also be present at screening: low C3, low C4, or anti-ds-DNA elevated to above normal range.
 8. Acceptable screening laboratory values:
 - a) Adequate hematologic criteria:
 - Absolute neutrophil count $\geq 1.5 \times 10^9/L$ ($\geq 1 \times 10^9/L$ if neutropenia is attributable to lupus disease activity)
 - White blood cells $\geq 2.0 \times 10^9/L$ ($\geq 1.5 \times 10^9/L$ if leukopenia is attributable to lupus disease activity)
 - Absolute lymphocyte count $\geq 0.5 \times 10^9/L$
 - Hgb ≥ 9 g/dL (≥ 8 g/dL if anemia is attributable to lupus disease activity)
-

-
- Platelet count $\geq 100 \times 10^9/L$ ($\geq 25 \times 10^9/L$ if thrombocytopenia is attributable to lupus disease activity)
- b) Adequate hepatic function:
- Total bilirubin $\leq 1.5 \times ULN$ ($3 \times ULN$ for patients with known Gilbert's syndrome)
 - AST $\leq 2.5 \times ULN$
 - ALT $\leq 2.5 \times ULN$
- c) eGFR ≥ 30 mL/min/1.73 m² estimated based on CKD-EPI formula
- d) IgG ≥ 500 mg/dL
9. Female patients of childbearing potential must have a negative serum pregnancy test at Screening and a negative urine pregnancy test at Baseline and must agree to employ adequate birth control measures for the duration of the study. Women of childbearing potential (WOCBP) must use highly effective and medically acceptable methods of contraception to prevent pregnancy during Screening and must agree to continue to practice adequate contraception during the study and for 4 weeks after administration of the last dose of the study drug.

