8.2.6.5 Proteinuria Evaluation

Proteinuria will be assessed via spot UPCR (should be first morning void in all patients with nephritis) and 24-hour urine collection (Phase 1b patients with nephritis and all Phase 2 patients).

Patients should be given specific instructions on the 24-hour urine collection. At a minimum, patients should be instructed to collect urine over a 24-hour period, to keep the sample cold during the collection period and until the sample is returned to the study site, and to return the sample (within 7 days after collection completed for screening).

At screening, patients will be instructed to collect two 24-hour urine collection samples, at least 7 days apart. Both samples must demonstrate UPCR levels meeting protocol inclusion in order to be eligible for Phase 2 study entry. If one of these samples fails to demonstrate UPCR levels meeting protocol inclusion for Phase 2, one additional 24-hour urine collection sample may be obtained at least 7 days from the last sample taken. In addition, a first morning void sample will also be collected at these same time points for a spot UPCR.

Once enrolled into the Phase 2 portion, 24-hour urine samples will be collected at Weeks 1, 5, 9, 13, 17, 21, 25, 29, 33, and 37. Patients should be instructed to return the chilled 24-hour urine sample to the clinic following its collection, which should occur during the 48 hours prior to the visit. A first morning void sample should also be collected at these same time points for a spot UPCR.

The 24-hour urine collection sample will be used to assess UPCR level at the specified visits. If the laboratory test results indicate a urine collection sample is inadequate at any time point, the spot UPCR obtained from the first morning void sample may be used instead for assessments performed at randomization and onward.

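### The UPCR part of partial renal response can be met by crossing 1.0 or 3.0 with no minimum fall, which conflicts with the 50% rule in section 11.3.5

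*Combined protocol and SAP*

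**What the plan says.** Section 11.1.2 lists the number of patients with PRR at 24 weeks, and time to PRR, as Phase 2 secondary endpoints. PRR has three criteria.

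- **(a) UPCR, lower stratum:** "A 50% reduction of UPCR and/or reduction of UPCR to < 1.0 if the baseline UPCR was < 3.0". The synopsis has the same rule: "A 50% reduction of UPCr and/or reduction of UPCr to < 1.0 if the baseline UPCr was < 3.0".
- **(a) UPCR, upper stratum:** "a 50% reduction of UPCR and/or reduction of UPCR to < 3.0 if the baseline was ≥ 3.0".
- **(b) eGFR:** at least 60 mL/min/1.73 m², or "no worsening of eGFR from baseline of" 25% or more.
- **(c) Medication:** "No use of prohibited medication".

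The entry criterion (section 5.2.3, criterion 5) is "Active nephritis with UPCR ≥ 1.0 measured in 24-hour urine collection". Section 8.2.6.5 applies it to two screening collections: "Both samples must demonstrate UPCR levels meeting protocol inclusion in order to be eligible for Phase 2 study entry". One further collection is allowed if one of the two fails. No floor is set for the Week 1 collection.

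The efficacy analysis text in section 11.3.5 gives a different rule: "Renal response will be classified as complete, partial [50% reduction in UPCR], or no renal response". It has no threshold limb.

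**The concern.** Criterion (a) joins a relative fall and an absolute threshold by *and/or*, so the threshold alone is enough. In the lower stratum that threshold is the value patients had to reach to enter the trial. Many patients may therefore start just above it, and a small downward fluctuation carries them across. A patient whose Week 1 value is already below 1.0 meets the limb with any fall at all.

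The rule also orders patients oddly: 2.95 to 1.50, a 49% fall, fails criterion (a), while 3.05 to 2.95 passes.

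Phase 2 is a single open-label arm of 20 patients. No control group is available to show how much of a PRR rate is urine variation around 1.0 or 3.0. Sections 2.5 and 2.5.3 say that Phase 2 results will inform later studies, so an inflated PRR rate could carry forward into their planning.

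**Working it through.** The plan states no expected PRR rate, so there is no figure to reproduce.

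**Inputs from the documents.** Thresholds and strata (11.1.2, synopsis); entry floor 1.0 (5.2.3); two screening collections with one retest (8.2.6.5); on-study collections at Weeks 5, 9, 13, 17, 21 and 25 (8.2.6.5); 20 patients (5.1).

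**Step 1: where the threshold is easier than a 50% fall.** Reaching threshold T from baseline b needs a fall of just over 1 − T/b. This is below 50% when b < 2T.

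- T = 1.0 (baseline < 3.0): easier for baselines below 2.0. From 2.0 to < 3.0, reaching < 1.0 already means more than a 50% fall.
- T = 3.0 (baseline ≥ 3.0): easier for baselines from 3.0 to < 6.0. From 6.0 upward it adds nothing.

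**Step 2: cases.** Fall = (baseline − follow-up)/baseline.

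| Baseline → follow-up | Fall | Meets (a) as written | Meets a 50% rule |
|---|---|---|---|
| 1.05 → 0.95 | 9.5% | yes | no |
| 1.50 → 0.99 | 34.0% | yes | no |
| 2.95 → 1.50 | 49.2% | no | no |
| 3.05 → 2.95 | 3.3% | yes | no |
| 2.50 → 1.20 | 52.0% | yes | yes |

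**Step 3: chance of crossing with no true change, at a given baseline.** Assume log-normal error in both readings, with a within-patient CV that the documents do not give. With s = √ln(1 + CV²), the chance of falling below T is Φ(ln(T/b)/(√2·s)). The chance of a fall of at least 50% is Φ(ln 0.5/(√2·s)). For example, at b = 1.2 and CV 20%, s = 0.198 and Φ(−0.182/0.280) = 25.8%.

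| | CV 10% | 20% | 30% | 40% |
|---|---|---|---|---|
| b = 1.05, below 1.0 | 36.5% | 43.1% | 45.3% | 46.4% |
| b = 1.2, below 1.0 | 9.8% | 25.8% | 33.0% | 36.9% |
| b = 1.5, below 1.0 | 0.2% | 7.4% | 16.4% | 22.8% |
| b = 4.0, below 3.0 | 2.1% | 15.2% | 24.4% | 29.9% |
| any b, fall ≥ 50% | 0.0% | 0.7% | 4.75% | 10.2% |

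**Step 4: averaged over an enrolled population.** Simulation with 400,000 draws per setting, no drug effect, the screening rule of 8.2.6.5, baseline taken as the Week 1 value, and independent errors. Assumptions not in the documents: median UPCR 1.5–3.0 and between-patient log SD 0.5–0.7. Columns give the within-patient log SD.

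| | 0.2 | 0.3 | 0.4 |
|---|---|---|---|
| Week 25, criterion (a) as written | 9–11% | 14–18% | 20–24% |
| Week 25, fall ≥ 50% | 0.7% | 5% | 11% |
| Any of six visits, (a) as written | 23–30% | 39–47% | 52–60% |
| Any of six visits, fall ≥ 50% | 3% | 19% | 34–35% |

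Between 1% and 15% of enrolled patients have a Week 1 value already below 1.0. In 20 patients the Week 25 rates correspond to 20 × 0.09 = 1.8 up to 20 × 0.24 = 4.8 patients under the written rule, against 20 × 0.007 = 0.1 up to 20 × 0.11 = 2.2 under a 50% rule.

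The simulation covers criterion (a) only. Criteria (b) and (c) can only remove patients, so the rates are upper bounds for PRR. The any-visit rows also assume that a single unconfirmed visit counts, which the documents do not define for time to PRR.

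**The case against.** Several points on the other side stand.

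- **Criterion (a) is not PRR.** A reader might infer that 1.05 to 0.95 is by itself a partial renal response. It is not, because the eGFR and medication criteria must also hold. Neither sets a size for the UPCR change, however, so a stable patient on stable medication passes both.
- **The primary result is safe.** A reader might also infer that the headline efficacy result is inflated. The documents do not support that: the primary endpoint is a 50% reduction, and its exact binomial test against 20% has no threshold limb. PRR is secondary, with no stated test.
- **The problem is bounded.** It is confined to the baseline ranges in Step 1.
- **Part of it is already visible.** The 50% count, time to a 50% fall, UPCR ≤ 0.5 and complete response are all reported. Setting PRR beside them would show much of the gap, though not the threshold-only count.
- **The operative rule may lie elsewhere.** Section 11.3.1 gives the SAP precedence and 11.3.5 refers to it for detail. No separate SAP text is in the material reviewed, so its PRR rule could not be checked.
- **Changing *and/or* to *and* is not a sound repair.** It would deny PRR to primary-endpoint responders such as 2.5 to 1.2 (52% fall) and 2.95 to 1.05 (64% fall). With an assumed true fall of 55%, about 3–14% of simulated patients had a fall of at least 50% but failed that stricter rule at Week 25. It would also match neither 11.1.2 nor 11.3.5.

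**Conclusion.** The point holds as a defect in a secondary endpoint definition. As written in 11.1.2 and the synopsis, criterion (a) can be met with a negligible fall, and 11.3.5 would classify the same patients differently. This rests on the ordinary inclusive reading of *and/or*.

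That trivial changes qualify follows from the text alone. The frequency does not: the Week 25 contrast of about 9–24% against 0.7–11% depends on assumed UPCR levels and variability, and it ignores the eGFR and medication criteria. What is at stake is the interpretation of the PRR rate and time to PRR in an uncontrolled arm of 20, not the primary inference. The correction is worth making because it is cheap.

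**What to change.** Reconcile 11.1.2 and the synopsis with 11.3.5 so that PRR requires a UPCR fall of at least 50% plus the existing eGFR and medication criteria. Do not make the < 1.0 or < 3.0 threshold mandatory. Apply the same rule to time to PRR, and carry the wording into the SAP.

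If the *and/or* wording is kept, report patients who qualify through the threshold alone as a separate row, and show PRR and time to PRR with and without them.

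Either route uses data already collected and changes only wording and tables. The cost is a somewhat lower reported PRR rate under the first route, or the extra row and the paired presentation under the second.
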